3.3.3 Women of Childbearing Potential

Women of childbearing potential (WOCBP) is defined as any female who has experienced menarche and who has not undergone surgical sterilization (hysterectomy or bilateral oophorectomy) and is not postmenopausal. Menopause is defined as 12 months of amenorrhea in a woman over age 45 in the absence of other biological or physiological causes. In addition, females under the age of 55 years must have a documented serum follicle stimulating hormone, (FSH) level $> 40 \text{ mIU/mL}$ to confirm menopause.

Females treated with hormone replacement therapy, (HRT) are likely to have artificially suppressed FSH levels and may require a washout period in order to obtain a physiologic FSH level. The duration of the washout period is a function of the type of HRT used. The duration of the washout period below are suggested guidelines and the investigators should use their judgment in checking serum FSH levels. If the serum FSH level is $> 40 \text{ mIU/ml}$ at any time during the washout period, the woman can be considered postmenopausal.

- 1 week minimum for vaginal hormonal products (rings, creams, gels)
- 4 week minimum for transdermal products
- 8 week minimum for oral products

Other parenteral products may require washout periods as long as 6 months.

3.3.4 *Criteria for Long-Term Extension*

Subjects who enter the short-term period according to the eligibility criteria outlined in Sections 3.3.1 and 3.3.2, and who complete 24 weeks on study medication are eligible for participation in the LTE period. The LTE period will remain blinded but will no longer be placebo controlled, as subjects completing Day 169 in the placebo arm will be re-randomized to existing active arms.

A separate informed consent must be signed to enter the LTE period.

The class and dose of background therapies is recommended to remain the same as in the short term period. However, temporary rescue therapy with prednisone (or prednisone equivalent) to transiently manage SLE disease activity may be instituted. The increase in prednisone should not exceed a total daily dose of 20 mg, and must return to the previous stable dose within 14 days. Subjects requiring more than 14 days of rescue therapy will be discontinued.

The use of cyclophosphamide, any intravenous, any intra-articular or biologic agent remains prohibited during LTE. Any changes to or new concomitant therapies must be recorded on the CRF.

[REDACTED]

3.4.2 *Other Restrictions and Precautions*

Active SLE and its treatment are associated with increased risk of infection. Subjects should be provided information about the signs of the most common serious infections (eg, pneumonia, sepsis) and must have the knowledge and means to access appropriate medical care.

3.5 *Discontinuation of Subjects following any Treatment with Study Drug*

Subjects MUST discontinue investigational product (and non-investigational product at the discretion of the investigator) for any of the following reasons:

- Subject's request to stop study treatment and/or participation in the study
- Any clinical adverse event (AE), laboratory abnormality or intercurrent illness which, in the opinion of the investigator, indicates that continued participation in the study is not in the best interest of the subject
- Termination of the study by Bristol-Myers Squibb (BMS)
- Loss of ability to freely provide consent through imprisonment or involuntarily incarceration for treatment of either a psychiatric or physical (eg, infectious disease) illness
- Unblinding a subject for any reason (emergency or non-emergency)
- Development of new active manifestations of lupus requiring treatment with any non-protocol approved medications during the study.
- Inability or subject's failure to comply with the protocol requirements.
- Subject who misses more than 3 consecutive weekly doses.
- Pregnancy
- Treated with prednisone (or prednisone equivalent) at a total daily dose exceeding 20 mg and/or for more than 7 days (short-term period) or more than 14 days (long-term extension period).

Patients should discontinue from study, perform End of Treatment and Follow-up Day 42 visits, and receive standard of care according to local guidelines.

In the case of pregnancy, the investigator must immediately notify the BMS Medical Monitor/designee of this event. If any female subject becomes pregnant she will be immediately discontinued from the study.

All subjects who discontinue investigational product should comply with protocol specified follow-up procedures as outlined in Section 5. The only exception to this requirement is when a subject withdraws consent for all study procedures including post-treatment study follow-up or loses the ability to consent freely (ie, is imprisoned or involuntarily incarcerated for the treatment of either a psychiatric or physical illness).

If study drug is discontinued prior to the subject's completion of the study, the reason for the discontinuation must be documented in the subject's medical records and entered on the appropriate CRF page.

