*Subjects who are receiving mycophenolic acid/mycophenolate mofetil may participate in the study only if mycophenolate mofetil therapy is given as a maintenance therapy and up to a maximum of 2 g/day (or mycophenoate acid dose equivalent); in subjects of African ancestry, 3 g/day (or mycophenoate acid dose equivalent) may be administered at the Investigator’s discretion.

v) Prednisone is not required; however, if subject is taking prednisone (or prednisone-equivalent), dose cannot exceed 30 mg/day at screening for a subject to be eligible and must be stable at a maximum of 10 mg/day for at least 5 days prior to Day 1 (randomization). Refer to Appendix 1 for a list of prednisone-equivalents.

vi) Any other immunosuppressive or biologic drug will require washout periods indicated in Appendix 2 prior to signing consent.

vii) If subjects receive chronic therapy with NSAIDs (including marketed COX-2 inhibitors), doses must be stable for 14 days prior to first dose of study medication on Day 1 (randomization) and are recommended to remain stable throughout the study.

Note: NSAIDs should be withheld for at least 12 hours prior to visits where BILAG, SLEDAI 2K, joint counts, CLASI and MDGA will be assessed.

3. Age and Reproductive Status

- a) Males and Females, ages 18 to 70 years, inclusive
- b) Women of childbearing potential (WOCBP) must have a negative serum or urine pregnancy test (minimum sensitivity 25 IU/L or equivalent units of HCG) within 24 hours prior to the start of study drug.
- c) Women must not be breastfeeding
- d) WOCBP must agree to follow instructions for method(s) of contraception for the duration of treatment with study drug(s) BMS-931699 plus 5 half-lives of study drug

BMS-931699 (7 days) plus 30 days (duration of ovulatory cycle) for a total of 65 days post-treatment completion.

- e) Males who are sexually active with WOCBP must agree to follow instructions for method(s) of contraception for the duration of treatment with study drug(s) BMS-931699 plus 5 half-lives of the study drug (7 days) plus 90 days (duration of sperm turnover) for a total of 125 days post-treatment completion.
- f) Azoospermic males and WOCBP who are continuously not heterosexually active are exempt from contraceptive requirements. However they must still undergo pregnancy testing as described in this section.

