4.5.3 Corticosteroids (Prednisone or Prednisone Equivalent) Dosing

- Prior to Randomization: Corticosteroids (prednisone or prednisone equivalent; refer to Appendix 1) may be used in accordance with the Investigator's clinical judgment and best standard of care. A maximum daily dose of 30mg/day is acceptable to be eligible for the

study and start screening; however, daily dose must be tapered down to a maximum of 10mg/day for at least 5 days prior to Day 1 (randomization day).

- Study Day 1 (randomization day): subjects requiring the use of prednisone (or prednisone equivalent) will be on a maximum dose of 10mg/day.
- Post Day 1 (after initiation of study therapy):
 - For subjects who flare or need to increase their prednisone (or prednisone equivalent) to control disease activity a one-time increase of up to a maximum daily dose of 20 mg/day for up to 2 consecutive days will be allowed to transiently manage disease activity.
 - A subject who requires a total daily dose of prednisone (or prednisone equivalent) exceeding 20 mg/day or who has another flare after the first rescue therapy, will be considered a treatment failure.
 - A subject who meets the treatment failure criteria as described above may continue on study medication; however, a subject requiring more than 20 mg/day of prednisone (or prednisone equivalent) for more than 7 days in the short-term period, or more than 14 days in the long-term extension period, will be discontinued.

Tapering of steroids during the course of the study is encouraged and should be evaluated at all visits. Once subject has received the first dose of study drug, prednisone (or prednisone-equivalent) may be tapered down at the discretion of the Investigator.

4.5.4 *Rescue Therapy*

4.5.4.1 *Short- Term Period*

A one-time increase of up to a maximum daily dose of 20 mg/day for up to 2 consecutive days will be allowed to transiently manage disease activity and will not be considered a treatment failure.

- A subject who requires a total daily dose of prednisone (or prednisone equivalent) exceeding 20 mg/day or who has another flare after the first rescue therapy, will be considered a treatment failure.
- A subject who meets the treatment failure criteria based on prednisone use may continue on study medication; however, a subject requiring more than 20 mg/day of prednisone (or prednisone equivalent) for more than 7 days in the short-term period, will be discontinued.

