- c) added that Placebo injection only applies to the Short-Term period of the study

33. Section 4.5.2 Dose modifications: clarified the management of the dose modifications

34. Section 4.5.3 Corticosteroids (Prednisone or Prednisone Equivalent) Dosing: clarified the management of dose modifications during the study

35. Section 4.5.4 Rescue Therapy: new section added for clarity on protocol allowance as rescue therapy and to define when subjects who require rescue therapy will be discontinued.

36. Section 4.6.2 Unblinding of the Study Sites: removed the last 2 paragraphs since the information was not pertaining to the unblinding of the study sites

37. Section 5.1 Flow Chart/Time and Events Schedule:

- a) Table 5.1-1 Screening Procedural Outline (IM128027): corrected Notes for ACR criteria for SLE form to be Appendix 3
- b) Table 5.1-1 Screening Procedural Outline (IM128027): corrected Procedures to add that breast/cervical cancer screening must also be documented
- c) Table 5.1-1 Screening Procedural Outline (IM128027): removed Ro (SS-A), La (SS-B), RNP and APL from samples collected at screening as these assessments are not required for eligibility
- d) Table 5.1-2 Short-Term Procedural Outline (IM128027): updated to clarify the +/- 2 days window also applies to Day 1 visit
- e) Table 5.1-2 Short-Term Procedural Outline (IM128027): removed Total soluble CD28 from procedures performed during the study
- f) Table 5.1-2 Short-Term Procedural Outline (IM128027): added a footnote to specify when the 42 days Follow Up visit should be conducted
- g) Table 5.1-3 Long-Term Extension Procedural Outline (IM128027): new table to outline procedures for LTE

38. Section 5.2 Study materials: updated to remove the requirement for a refrigerated centrifuge
39. Section 5.3.2 Laboratory Test Assessments: updated to clarify the laboratory tests being assessed, to include the LTE and add HIV screen at the screening visit only (since this was omitted in the initial version of the protocol)
40. Section 5.3.3 Tuberculosis Screening and Chest X-Ray: updated to clarify that a confirmed negative IGRA test is required prior to Day 1
41. Section 5.4.1 Primary Efficacy Assessment: updated to include the LTE
 - a) Section 5.4.1.1 Short-Term Period: new section to separate the Short-Term Period Efficacy Assessment from the LTE
 - b) Section 5.4.1.2 Long-Term Extension Period: new section added to include the LTE

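### The mandatory steroid stop in Protocol 3.5 is defective because of its and/or wording, and the extension steroid rule and the pregnancy rule also differ between sections

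*Protocol*

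**What the plan says.** **Short-term steroids.** Protocol 3.5 is a list of reasons for which stopping investigational product is compulsory. One entry is "Treated with prednisone (or prednisone equivalent) at a total daily dose exceeding 20 mg and/or for more than 7 days (short-term period"; the same entry gives 14 days for the extension. Sections 4.5.3 and 4.5.4.1 deal with the same event differently. There, a total daily dose above 20 mg makes the subject a treatment failure, but "A subject who meets the treatment failure criteria based on prednisone use may continue on study medication", and only "a subject requiring more than 20 mg/day of prednisone (or prednisone equivalent) for more than 7 days in the short-term period, will be discontinued".

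**Background steroids.** Prednisone is permitted on study. Inclusion criterion 2c-v in 3.3.1 says it "must be stable at a maximum of 10 mg/day for at least 5 days prior to Day 1 (randomization", and 4.5.3 says that on Day 1 "subjects requiring the use of prednisone (or prednisone equivalent) will be on a maximum dose of 10mg/day".

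**Extension steroids.** Section 3.3.4 says "Subjects requiring more than 14 days of rescue therapy will be discontinued", with no dose condition. Section 4.5.3 applies its threshold of more than 20 mg/day to the extension too ("or more than 14 days in the long-term extension period, will be discontinued"), and 4.5.4.2 likewise needs more than 20 mg/day for more than 14 days. Both 3.3.4 and 4.5.4.2 cap rescue at 20 mg/day and require a return to the earlier stable dose within 14 days.

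**Pregnancy.** Sections 3.5 and 5.3.2 require discontinuation without exception. Section 6.4 repeats the requirement, then allows a pregnant subject to stay on study drug in rare cases after consultation with the sponsor. The extension schedule (Table 5.1-3) requires a confirmed negative pregnancy test in the 24 hours before dosing.

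**The concern.** These are operative stopping rules, to be applied at about 125 sites. If two sections give different answers for the same steroid course, one site may stop a subject whom another would keep on drug. A site that uses the permission in 4.5.4.1 breaches a compulsory rule in 3.5 if that rule is read literally.

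A stopped subject loses the remaining study drug, is sent to the End of Treatment and Follow-up Day 42 visits (3.5), and cannot enter the extension, which requires 24 weeks completed on drug (3.3.4). Under SAP 8.3, binary responses that cannot be assessed after discontinuation become non-response. CLASI response is exposed to this because, unlike BICLA and the SAP's SRI, it has no medication component that would already have failed the subject. The pregnancy text decides whether a pregnant subject may be dosed with an investigational drug.

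**Working it through.** The plan gives no figure on this point to reproduce. The check sets the rules side by side and then works out what a stop costs one subject.

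**1. Short-term rules applied to example courses**

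| Course | 3.5 read as *or* | 3.5 read as *and* | 4.5.3 / 4.5.4.1 |
|---|---|---|---|
| 10 mg/day, 8 days | stop | no stop | no stop |
| 15 mg/day, 10 days | stop | no stop | no stop |
| 20 mg/day, 2 days | no stop | no stop | no stop |
| 30 mg/day, 3 days | stop | no stop | treatment failure, may continue |
| 30 mg/day, 10 days | stop | stop | stop |

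Read as *and*, 3.5 agrees with the rescue sections in every row. Read as *or*, it differs in two regions: (a) above 20 mg/day for 1 to 7 days, and (b) 20 mg/day or less for more than 7 days. Region (b) takes in all permitted background use from day 8 of treatment.

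**2. Extension rules**

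| Course | 3.5 *or* | 3.5 *and* | 3.3.4 | 4.5.3 / 4.5.4.2 |
|---|---|---|---|---|
| 15 mg/day rescue, 20 days | stop | no stop | stop | no stop |
| 30 mg/day, 5 days | stop | no stop | no stop | no stop |
| 30 mg/day, 20 days | stop | stop | stop | stop |

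The first row is a conflict between 3.3.4 and 4.5.4.2 however 3.5 is read. That course also breaks the 14-day return requirement in both sections, but only 3.3.4 attaches discontinuation to it directly. The second row exceeds the 20 mg cap in both.

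**3. Pregnancy**

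Sections 3.5 and 5.3.2 say stop, and 6.4 says stop and then permits an exception. Neither 3.5 nor 5.3.2 mentions the exception, and a pregnant subject cannot meet the negative-test condition in Table 5.1-3.

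**4. Exposure lost by one subject who is stopped**

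Weekly doses fall on Days 1 + 7k, k = 0 to 23: 24 doses, the last on Day 162. Every-other-week (EOW) active doses, assuming active drug on Day 1, fall on Days 1 + 14k, k = 0 to 11: 12 doses, the last on Day 155.

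| Last dose | Weekly injections not given | EOW active injections not given |
|---|---|---|
| Day 29 | 24 − 5 = 19 | 12 − 3 = 9 |
| Day 85 | 24 − 13 = 11 | 12 − 7 = 5 |
| Day 113 | 24 − 17 = 7 | 12 − 9 = 3 |

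These counts hold for any discontinuation. They show what is at stake for a subject, not how often the conflict bites.

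**5. CLASI at Day 85**

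The Day 85 window is Days 72–99 (SAP Table 8.5-1), and assessments within 28 days of the last dose are kept (SAP 8.5). A last dose on Day 29 allows data up to 29 + 28 = Day 57, short of Day 72, so Day 85 becomes non-response. A last dose on Day 71 with an End of Treatment assessment on Day 78 is 7 days after dosing and inside the window, so it may supply the Day 85 value. The earliest last dose for which this is possible is 72 − 28 = Day 44. The Follow-up visit, about 42 days after the last dose, is outside the 28-day limit.

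**The case against.** The strongest reply is that the short-term conflict exists only if *and/or* is read as *or*, and that reading is absurd because it would remove everyone on background prednisone. The *and* reading agrees with 4.5.3 and 4.5.4.1, which answer the case above 20 mg/day expressly. This largely disposes of region (b): it is a drafting slip that no site is likely to apply. It does not dispose of region (a). Nothing odd follows from a compulsory stop above 20 mg/day, so a site could apply it in good faith. No visible text says which section prevails. Section 3.4.1, on restricted treatments, is blacked out and cannot be checked.

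Three further replies stand.

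- **Non-compliance entry.** The compulsory list in 3.5 also covers failure to comply with protocol requirements. An extension subject who misses the 14-day return is therefore arguably stoppable under 3.5 as well, so it would be too strong to say that only 3.3.4 can stop that subject.
- **Which extension rule is the outlier.** A reader might infer that 3.3.4 is the odd one out. That presupposes the *and* reading of 3.5; on the *or* reading, 3.5 agrees with 3.3.4 for 15 mg/day over 20 days. The 20 mg cap in both extension texts also sits oddly with a stop that applies only above 20 mg. The documents do not settle the choice.
- **Pregnancy.** The exception in 6.4 needs sponsor consultation, so variation between sites is unlikely. The contradiction in the text remains.

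**Conclusion.** The steroid entry in 3.5 is wrong as written and should be corrected. The extension threshold and the pregnancy rule are separate inconsistencies in current operative text. The effect is on study drug exposure, extension eligibility and safety conduct, at the level of the individual subject.

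Two stronger readings are tempting and are not supported.

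- **Bias in the primary endpoint.** In region (a) the subject is a treatment failure, and Protocol 5.4.1.1 makes absence of treatment failure part of BICLA. Provided that failure is carried to Day 169, the subject is a non-responder whether stopped or continued. The duration limb could alter BICLA only if a site stopped subjects on stable background prednisone, and nothing suggests that any would. The documents do not say how often such steroid courses occur, so no arm-level effect can be claimed. The extension analysis is descriptive.
- **Automatic CLASI non-response at Day 85 after any earlier stop.** An assessment on Days 72–99 within 28 days of the last dose may be used, so a stop shortly before Day 85 does not necessarily have this result.

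The conclusion rests on the visible text and on the ordinary meaning of *and/or* as including *or*.

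**What to change.** 1. **Protocol 3.5.** Strike *and/or* from the steroid entry, so that the duration qualifies the dose: above 20 mg/day for more than 7 days in the short-term period, or more than 14 days in the extension. This matches 4.5.3 and 4.5.4. Item 35 of Amendment 06 says that 4.5.4 was added partly "to define when subjects who require rescue therapy will be discontinued", so 3.5 should follow it.
2. **Extension threshold.** The sponsor should choose one rule and use it in 3.3.4, 3.5, 4.5.3 and 4.5.4.2. If the any-dose 14-day rule is chosen, the extension part of 3.5 must be worded accordingly and tied to rescue above the stable dose, so that it does not catch background prednisone. Do not add a statement that a missed 14-day return does not require discontinuation: no document supports it, and it would clash with the non-compliance entry in 3.5.
3. **Pregnancy.** Delete the continuation sentence in 6.4, or name it as the sole exception in 3.5, 5.3.2 and the pregnancy-test note in Table 5.1-3.

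The cost is a wording amendment to the protocol. The SAP, the sample size and the study procedures do not change.

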3.6 Post Study Drug Follow up

In this study, assessment of lupus disease activity is a key endpoint of the study. Post study follow-up is of critical importance and is essential to preserving subject safety and the integrity of the study. Subjects who discontinue study drug must continue to be followed for collection of outcome and/or survival follow-up data as required and in line with Section 5 until death or the conclusion of the study.

3.6.1 Withdrawal of Consent

Subjects who request to discontinue study drug will remain in the study and must continue to be followed for protocol specified follow-up procedures. The only exception to this is when a subject specifically withdraws consent for any further contact with him/her or persons previously authorized by subject to provide this information. Subjects should notify the investigator of the decision to withdraw consent from future follow-up **in writing**, whenever possible. The withdrawal of consent should be explained in detail in the medical records by the investigator, as to whether the withdrawal is from further treatment with study drug only or also from study procedures and/or post treatment study follow-up, and entered on the appropriate CRF page. In the event that vital status (whether the subject is alive or dead) is being measured, publicly available information should be used to determine vital status only as appropriately directed in accordance with local law.

3.6.2 Lost to Follow-Up

All reasonable efforts must be made to locate subjects to determine and report their ongoing status. This includes follow-up with persons authorized by the subject as noted above. Lost to follow-up is defined by the inability to reach the subject after a minimum of three documented phone calls, faxes, or emails as well as lack of response by subject to one registered mail letter. All attempts should be documented in the subject's medical records. If it is determined that the subject has died, the site will use permissible local methods to obtain the date and cause of death.

If investigator's use of third-party representative to assist in the follow-up portion of the study has been included in the subject's informed consent, then the investigator may use a Sponsor-retained third-party representative to assist site staff with obtaining subject's contact information or other public vital status data necessary to complete the follow-up portion of the study. The site staff and representative will consult publicly available sources, such as public health registries and databases, in order to obtain updated contact information. If after all attempts, the subject remains lost to follow-up, then the last known alive date as determined by the investigator should be reported and documented in the subject's medical records.

